[name]	Consultant Clinical Oncologist, Dept of Clinical Oncology, Royal Devon & Exeter NHS Trust, [name].
[name]	Statistician, Clinical Trials and Statistics Unit, Section of Clinical Trials, Institute of Cancer Research, [name].
[name]	Consultant Clinical Oncologist, Dept of Clinical Oncology, Royal Surrey County Hospital, [name].
[name]	Consultant Clinical Oncologist, Dept of Clinical Oncology, Ipswich Hospital, [name].
[name]	Consultant Clinical Oncologist, The Royal Marsden Hospital, [name].
[name]	Consultant Clinical Oncologist, Department of Clinical Oncology, Christie Hospital, [name].
[name]	Trial Coordinator, Clinical Trials and Statistics Unit, Section of Clinical Trials, Institute of Cancer Research, [name].
[name]	Consultant Clinical Oncologist, The Royal Marsden Hospital, [name].

TRIAL SUMMARY

Title	Prospective randomised clinical trial testing 5.7 Gy and 6.0 Gy fractions of whole breast radiotherapy in terms of late normal tissue responses and tumour control.	
Aim	To test 5 fractions of 5.7 Gy and 6.0 Gy against 25 fractions of 2.0 Gy in terms of late normal tissue effects and tumour control in women prescribed whole breast radiotherapy (no boost) after local excision of early breast cancer.	
Eligibility criteria	 Inclusion criteria i) Age ≥ 50 years ii) Invasive carcinoma breast iii) Breast preserving surgery iv) Pathological tumour size < 3.0 cm v) Complete microscopic resection vi) Axillary node negative Exclusion criteria i) Mastectomy ii) Lymphatic radiotherapy iii) Radiotherapy breast boost iv) Neoadjuvant or adjuvant cytotoxic therapy 	
Study design	Prospective randomised controlled clinical trial.	
Randomisation	Control arm:50.0 Gy in 25 fractions of 2.0 Gy over 35 daysTest arm 1:30.0 Gy in 5 fractions of 6.0 Gy over 35 daysTest arm 2:28.5 Gy in 5 fractions of 5.7 Gy over 35 days	
Radiotherapy delivery	Tangential fields to the whole breast; no boost; dosimetry must conform to ICRU 50/62 (+7%, -5%), no cardiac exposure.	
Endpoints	PrimaryChange in photographic breast appearance.Secondary endpointTumour recurrence in the breast.	
T		

1. TITLE

Prospective randomised clinical trial testing 5.7 Gy and 6 Gy fractions of whole breast radiotherapy in terms of late normal tissue responses and tumour control.

2. BACKGROUND

Human tumour responses are assumed to be insensitive to fraction size relative to dose-limiting late reacting normal tissues, a view that is consistent with the responses of animal tumours and human squamous carcinomas of the cervix uteri, lung and head and neck [12; 13; 17]. This means that as fraction size increases above 2.0 Gy, the gradient of the dose response curve is shallower for tumours than for late reacting normal tissues, a relationship highly unfavourable to cure. This relationship may not apply to all tumour types, though. An α/β value in the range 4 - 5 Gy was first estimated for the response of locally advanced and recurrent chest wall disease in the early 1950's and analysed using the linear quadratic model in the mid-1980's [3; 5]. More recently, a direct estimate of 4.1 Gy (95% CI 1.0 - 9.7) was reported for the fractionation sensitivity of breast The Royal cancer in Marsden Hospital/Gloucestershire Oncology Centre (RMH/GOC) Breast Fractionation Trial involving 1,410 patients [10]. If the high fractionation sensitivity of breast cancer is confirmed by the recent NCRI Standardisation of Radiotherapy (START) trial, the implications are that larger fraction sizes have no disadvantages, and perhaps have significant advantages, for women with early breast cancer.

Hypofractionation lends itself to acceleration, taking advantage of the relative sparing of early skin reactions as fraction size increases and the absence of a significant time dependency for late adverse effects. Tumour repopulation has recently been tested as a determinant of treatment outcome in the context of adjuvant systemic therapy. In a randomised comparison of conventional 3-weekly schedules of doxorubicin and cyclophosphamide with the same chemotherapy doses given at 2-weekly intervals (using growth factors to accelerate marrow recovery), the hazard ratios for disease-free and overall survival associated with 2-weekly chemotherapy were 0.74 (p = 0.01) and 0.69 (p = 0.01), respectively in 2,005 patients [2]. Recent reports of accelerated radiotherapy fractionation in head and neck cancer indicate that very modest shortening of treatment has a detectable impact on local control. In a trial of 1,476 patients randomised to 5 (control arm) or 6 (test arm) fractions per week of conventional radiotherapy, local tumour control in the test arm was 76% patients compared to 64% in the control group [9]. In this study, shortening treatment by only 7 days was associated with a 12% absolute reduction in local recurrence at the primary site, a reduction in the odds of recurrence of 16%. The implications for breast cancer are that modest reductions in treatment time may translate into worthwhile gains in tumour control without enhanced late normal tissue injuries. If the predicted late adverse effects of once-weekly 5.7 - 6.0 Gy fraction sizes are confirmed in the proposed FAST trial, it will encourage future evaluation of accelerated hypofractionated breast radiotherapy delivering 5 fractions over 1 - 2 weeks.

3. AIM

To test 5 fractions of 5.7 Gy and 6.0 Gy against 25 fractions of 2.0 Gy in terms of late normal tissue effects and tumour control in women prescribed whole breast radiotherapy (no boost) after local excision of early breast cancer.

4. ELIGIBILITY CRITERIA

Inclusion criteria

- i) Age ≥ 50 years
- ii) Invasive carcinoma breast
- iii) Breast preserving surgery
- iv) Pathological tumour size < 3.0 cm
- v) Complete microscopic resection
- vi) Axillary node negative

Exclusion criteria

- i) Mastectomy
- ii) Lymphatic radiotherapy
- iii) Radiotherapy breast boost
- iv) Neoadjuvant or adjuvant cytotoxic therapy.

5. **RANDOMISATION**

Control arm:	50.0 Gy in 25 fractions of 2.0 Gy over 35 days
Test arm 1:	30.0 Gy in 5 fractions of 6.0 Gy over 35 days
Test arm 2:	28.5 Gy in 5 fractions of 5.7 Gy over 35 days

The iso-effect relationships for these schedules are modelled in Appendix 1, based on the linear-quadratic model.

Entry procedure

Randomisation will be performed by telephone or facsimile to ICR-CTSU (web-based randomisation may become available during the life of the trial). Treatment allocation will be 1:1:1 and will use computer-generated random permuted blocks. Randomisation will be stratified by centre.

6. **RADIOTHERAPY**

General

The requirements defined below are regarded as the minimum, and should be adopted by all participants. Patients requiring lymphatic radiotherapy or breast boost should not be included in the trial. Both tangential fields to the whole breast must be treated with every fraction.

Breaks in the treatment due to bank holidays or equipment failure will be recorded but should not lead to modification of the radiotherapy dose or fractionation.

Patient position

The patient must lie supine and her position must remain unchanged during planning, simulation and treatment. The patient may lie on an inclined plane. Some form of immobilisation device, such as a breast board, is highly recommended. Reproducibility of the position should be verified by orthogonal laser beams.

Clinical target volume

Soft tissues of the whole breast down to the deep fascia, but not including underlying muscle and ribcage, nor overlying skin and excision scar.

Planning target volume

Entire breast with 1 cm margin to palpable breast tissue.

Medial and lateral borders should not normally extend beyond the anterior midline or the mid-axilla. It is desirable to reduce these margins in selected patients, if the tumour bed does not encroach, in order to reduce the volume of heart and/or lung in the high dose zone. Irradiation of the ribcage below the inframammary fold is unnecessary unless the tumour bed encroaches on this margin or the lower border of the breast overlaps the inframammary fold.

Deep margin extends down to the deep fascia, but the treatment volume inevitably includes pectoralis major and ribcage.

Field arrangement

Transverse cross-section of the patient is taken through the centre of the planning target volume using computerised tomography if possible; otherwise, an external contour is acceptable.

The maximum thickness of lung included in the tangential field is 2.0 cm, defined by computed tomography or simulator. Alternative verification of lung depth by machine films is acceptable. The anterior border of the field in free air should be at least 1 cm from the skin surface.

Cardiac shielding will be introduced using MLC or other shielding techniques.

Dose homogeneity & reference point

It is strongly recommended that the dose distribution across the target volume be modified to ensure a dose homogeneity within ICRU guidelines. If the maximum dose is > 107%, full dose compensation should be introduced where possible. Appendix 3 gives details of possible published methods and a description of a simple technique which may be adapted for either CT or multiple surface contour outlining.

Where full dose compensation is not technically possible, two further outlines are required in addition to the central contour; one at 1 cm inside the superior field border and one at 1 cm superior to the infra-mammary fold. These will give an indication of the likely maximum doses in the breast.

When calculating the dose distribution using a bulk density correction, the value used must be clearly stated.

Doses must be prescribed to the reference point which is at or near the centre of the target volume (ICRU 50). The point is half way between the lung surface and the skin surface on the perpendicular bisector of the posterior beam edge. Maximum and minimum doses must also be stated to describe dose homogeneity and the difference between these should be no more than 10% on the central plane and within ICRU guidelines over the whole breast where this data is available. Maximum doses in the superior plane and plane through the infra-mammary fold should be stated if full dose compensation is not used and only three outlines acquired.

Radiotherapy equipment

Megavoltage photons must be used. 4 - 6 MV photons are suitable for most patients. Tangential fields with large baseline separations may be best encompassed with 8 - 10 MV photons. Cobalt gamma-rays are not suitable.

7. FOLLOW-UP

A Case Report Form (CRF) booklet for each patient will be sent to the clinician after randomisation. The follow-up forms must be completed annually for 10 years (minimum 5 years).

8. ENDPOINTS

Primary endpoint Change in photographic breast appearance.

Secondary endpoint Tumour recurrence in the breast.

8.1 Assessments of endpoints

Primary endpoint: Photographic assessments of late adverse effects

Photographic assessments after breast conserving surgery will be taken at baseline, and at years 2 and 5. Timing of assessments is based on experience from the START trial, with the aim of maximising the information collected whilst minimising the assessment burden. Two frontal views of the chest will be taken, one with hands on the hips and the other with hands raised as far as possible above the head. Both photographs will exclude the head. Digital images (as for IMPORT) are acceptable.

Change of breast appearance compared with the post-surgical baseline will be scored on a three-point graded scale together with an assessment of breast size and surgical deficit. All photographs will be taken and stored locally in the first instance. Periodically, all photographs will be collected and assessed blind by a select group of observers. Reliability and repeatability of the assessments will be verified. The feasibility of and procedures for this scoring mechanism have been established in the START trial and assessment will continue using existing criteria.

Secondary endpoint: Tumour recurrence in the breast

Tumour relapse and new ipsilateral primary tumour must be confirmed by pathological assessment. Metastases will be determined by an appropriate combination of clinical, haematological, imaging and pathological assessment, recognising that pathological confirmation is not always possible.

Local tumour recurrence / ipsilateral new primary tumour defined as:

i) Breast parenchyma / skin within whole breast volume.

The following events will be recorded, but do not constitute secondary endpoints:

- i) Regional metastases (axilla, supraclavicular fossa, internal mammary chain).
- ii) Haematogenous metastases (only details of the first relapse are required).
- iii) Death.

9. ANALYSIS AND STATISTICAL CONSIDERATIONS

9.1 Sample size

The proportion of women recording any late change in breast appearance will be compared between trial arms. Assuming a α/β value of 3.5 Gy (average of 3.0 and 4.0 Gy for late effects), the two test regimens correspond to the delivery of 48 Gy and 52 Gy, respectively, in 2.0 Gy equivalents. Assuming the same α/β value, the two test schedules tested in the RMH/GOC Breast Fractionation Trial (39 Gy and 42.9 Gy in 13 fractions) are equivalent to 46 Gy and 53 Gy in 2.0 Gy equivalents. These two dose levels were associated with 13% and 28% rates, respectively, of change in breast appearance at 24 months. Assuming an average of 20% of women develop an

observable change in breast appearance 24 months after the proposed test arms, randomisation of 900 patients (300 per treatment arm) will allow an absolute 10% difference in the probability of a change in breast appearance between the two test dose levels to be detected with 90% power at the 5% significance level (2-sided test). Assuming linearity between the two dose levels of the test arms, the analysis would also allow interpolation (and limited degrees of projection or extrapolation if necessary) to determine the experimental schedule equivalent to daily fractions of 2.0 Gy. The estimate of sample size allows for 10% loss to follow-up.

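### The sample size does not give the stated 90% power: 300 per arm with 10% loss gives about 83%, and 90% would need about 372 per arm

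*Protocol*

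**What the plan says.** Section 9.1 sizes the trial on the proportion of women with any late change in breast appearance. The planning rate is a 20% average, and it refers to an "observable change in breast appearance 24 months after the proposed test arms". The section then claims that "randomisation of 900 patients (300 per treatment arm) will allow an absolute 10% difference in the probability of a change in breast appearance" to be shown. The contrast meant is one test schedule against the other, and the difference is "to be detected with 90% power at the 5% significance level (2-sided test"). The section closes with "The estimate of sample size allows for 10% loss to follow-up". Section 5 fixes the split: "Treatment allocation will be 1:1:1". The two test arms are therefore equal in size, and the 300 per arm already includes the women expected to be lost.

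**The concern.** Power, significance level, sidedness, average rate, difference, loss and sample size are all given, so any one of them can be checked against the rest. They do not agree: 300 per arm is too few for the stated target.

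This is the protocol's only power statement, and it concerns the primary endpoint. Section 9.1 also uses the same pair of dose levels to interpolate the schedule equivalent to 2.0 Gy fractions. If the two test arms are not separated statistically, readers will judge that result against a claimed 10% chance of missing a 10-point difference. If the real chance is 17%, the null result is weaker evidence than the protocol says. The monitoring committee may advise recruiting beyond the planned number (section 9.3), and that judgement should also rest on the true power.

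**Working it through.** **Inputs (section 9.1, allocation from section 5).** Average rate 20% at 24 months, absolute difference 10 points, two-sided 5%, power 90%, 300 per arm, 10% loss. The individual rates are not printed. An average of 20% and a difference of 10 points give p1 = 0.15 and p2 = 0.25. Evaluable per arm: 300 × 0.9 = 270.

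**Plausibility of the pair.** Section 9.1 quotes 13% at 46 Gy and 28% at 53 Gy from the earlier fractionation trial, a slope of 15/7 = 2.14 points per Gy. At the stated 48 and 52 Gy this gives about 17% and 26%, close to 15% and 25%.

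**Number needed for 90% power** (pooled variance under the null):

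n = [1.960 × √(2 × 0.20 × 0.80) + 1.2816 × √(0.15 × 0.85 + 0.25 × 0.75)]² / 0.10²

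= [1.960 × 0.5657 + 1.2816 × 0.5612]² / 0.01 = (1.1087 + 0.7193)² / 0.01 = 334.2, so 335 evaluable per arm.

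After 10% loss: 334.2 / 0.9 = 371.3, so 372 per arm and 1,116 in total under 1:1:1. Rounding to 335 before dividing gives 373 and 1,119.

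**Power actually provided:**

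- n = 270: z = (0.10 × √270 − 1.1087) / 0.5612 = (1.6432 − 1.1087) / 0.5612 = 0.952, power 83.0%.
- n = 300 (no loss): z = (1.7321 − 1.1087) / 0.5612 = 1.111, power 86.7%.

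**Detectable difference.** With 270 per arm and rates centred on 20%, 90% power is reached at 11.1 points.

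**Other methods, two-sided 5%, 15% v 25%:**

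| Method | Power at 270 per arm | Power at 300 per arm |
|---|---|---|
| Pooled two-proportion | 83.0% | 86.7% |
| Unpooled variance | 83.3% | 87.0% |
| Arcsine | 83.3% | 86.9% |
| Continuity-corrected | 80.1% | 84.3% |
| Logrank (Schoenfeld) | 84.3% | 87.9% |

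For the logrank row, the hazard ratio is ln 0.75 / ln 0.85 = 1.77 and the events are 0.40 × 270 = 108. Then z = ½ × √108 × ln 1.77 − 1.96 = 1.007.

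**Which inputs would give 300?**

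| Inputs | Evaluable per arm for 90% | With 10% loss | Power at 270 | Conflict with the text |
|---|---|---|---|---|
| 15% v 25%, one-sided 5% | 272.2 | 302.4 | 89.8% | test stated as two-sided |
| 10% v 20%, two-sided 5% | 265.9 | 295.4 | 90.4% | average is 15%, not 20% |
| 20% v 30%, two-sided 5% | 392 | 436 | 76.7% | average is 25%, not 20% |

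The first two rows come close to the printed number, but each contradicts a printed input. The third treats 20% as the lower rate and makes the shortfall larger.

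**The case against.** - **The pair 15% v 25% is inferred.** The sponsor may have computed correctly for 10% v 20% and misdescribed the rate. That is possible, but 10% v 20% contradicts the printed average and sits below the 13% and 28% quoted as the basis. On that reading a printed input is still wrong.
- **Section 9.2 names a logrank test, not a comparison of proportions.** This is correct, and it moves the figure from 83% to 84%. Even with no loss, the logrank power is 87.9%.
- **The control arm does not enter the sized comparison.** The deficit in the two test arms is 2 × 72 = 144 women. The total of 3 × 72 = 216 follows only because allocation is 1:1:1. Both figures are right for what they describe.
- **The practical effect is modest.** Power stays above 80%, and the detectable difference moves from 10 to 11.1 points. The planned estimates, confidence intervals and interpolation do not depend on nominal power. This limits the consequences but does not make the stated figure correct.

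**Conclusion.** The power statement is wrong as written. With the printed inputs, 900 patients give about 83% power (80% to 84% across methods), not 90%. The type II error is about 17%. Keeping 90% for a 10-point difference would take about 372 per arm, or 216 more patients in total under 1:1:1.

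The result rests on reading the stated average and difference as 15% v 25%, and on taking the 10% loss as included in the 300. The second assumption is not decisive, because no method in the table reaches 90% even without loss. A one-sided critical value may have been used by mistake, since it reproduces the number almost exactly, but the document does not show this. The trial is not invalidated. Its stated sensitivity is overstated.

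**What to change.** Replace the power sentence in section 9.1 with one to this effect: 900 patients (300 per arm, 270 evaluable after 10% loss) give about 83% power, by a two-sided 5% comparison of two proportions, to detect 15% v 25% between the test arms, or 90% power for an 11-point difference centred on 20%. If power is to be quoted for the logrank test of section 9.2 instead, the figure for 15% v 25% is about 84%.

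Print the two assumed rates. If the sponsor's calculation used other rates, state those and their basis, and correct the 20% average. The sidedness should not be changed simply to keep the 90%.

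The cost is one sentence and a less favourable power figure, with no extra patients. Keeping 90% for a 10-point difference would instead mean raising the target to about 1,116.

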9.2 Analysis

The principal analysis (late radiation effects on normal tissues and tumour recurrence) will be a logrank comparison of time from randomisation to the endpoint of interest by allocated treatment for all randomised patients (i.e. intention to treat). Incidence of late normal tissue effects will be analysed at two (primary analysis) and five years. For tumour recurrence, the primary endpoint is at five years. Survival analyses will assume that relapses before and after five years will be included in the analysis accordingly (i.e. patients will be followed from randomisation until it becomes impractical to do so further, and patients will only be censored in the analysis upon death or if lost to follow-up).

Analyses will compare fractionation schedules and will estimate the size of treatment effect with a confidence interval for the estimated difference between schedules. Information will be provided on both the absolute and relative treatment effect.

The incidence of uncommon complications will be monitored.

9.3 Interim analyses and data monitoring

Interim analyses of local tumour control, normal tissue responses, radiotherapy sideeffects and the other endpoints will be conducted at yearly intervals and presented to an independent Data Monitoring and Ethics Committee (DMEC) for confidential review. In the light of the interim analyses, the DMEC will advise the Steering Committee if, in their view, the trial has indicated "proof beyond reasonable doubt" that one of the schedules is clearly indicated or contraindicated in terms of late radiation effects. In reviewing the evidence, the DMEC will also consider any available data from other randomised trials involving similar comparisons. The Steering Committee may then consider modification or termination of the study. Unless such a situation arises, the Steering Committee, the Trial Management Group, the collaborators and the central administrative staff (except the statistician who prepares the analyses) will remain unaware of the interim results. The DMEC may recommend continuation beyond the planned number of patients in the trial if it is felt that further information is required to address reliably the hypothesis in question.

9.4 **Publication & Presentation**

The success of the trial depends entirely on the participation by a large group of clinical oncologists. The main results of the trial will therefore be published in the name of the trial on behalf of all collaborators. All participants will be listed under the name of their hospital, together with the total number of patients entered.

10. ETHICS COMMITTEE APPROVAL

This trial has been approved by South West Multi-Centre Research Ethics Committee (NHS REC No 04/MRE06/17). Participants will also need the approval of their Local Research Ethics Committee. See Appendix 2 for patient information sheets, general practitioner information letter and patient consent forms.

11. PATIENT INFORMATION

The importance of providing a high level of information to patients is recognised. Patients will be informed of the services offered by cancerbackup in the trial information leaflets. The publications we aim to provide include Clinical Trials (booklet prepared by The Royal Marsden NHS Foundation Trust) and Breast Cancer (booklet prepared by cancerbackup). Local leaflets on radiotherapy should also be provided, but these must be approved by the appropriate committees before distribution. Each patient invited into the trial will receive an information sheet explaining the study in detail. In addition, the long-term side effects of radiotherapy to the breast area and the likelihood of these developing post treatment will be explained. We will ask for your permission to inform your GP about the study and your participation in it.

